## 5.2 Exclusion Criteria

Subjects with any of the following will be excluded from the study:

1. Known infection with HIV, HCV, or HBV. This information will be obtained verbally from the patient.
2. If female, active pregnancy or breast-feeding or plans to become pregnant during study participation.
3. Chronic medical conditions that cause immunodeficiency or that require medications which could alter immune function such as immunosuppressants and immunoenhancers.
4. Have any medical disease or condition that, in the opinion of the site principal investigator or appropriate sub-investigator, is a contraindication to study participation. This includes any chronic medical disease or condition, defined as persisting 3 months (defined as 90 days) or longer, that would place the subject at an unacceptable risk of injury, render the subject unable to meet the requirements of the protocol, or may interfere with the evaluation of responses or the subject's successful completion of this study
5. Have an acute illness, as determined by the site principal investigator or appropriate sub-investigator, within 72 hours prior to study vaccination. An acute illness which is nearly resolved with only minor residual symptoms remaining is allowable if, in the opinion of the site principal investigator or appropriate sub-investigator, the residual symptoms will not interfere with the ability to assess safety parameters as required by the protocol.
6. Persons taking anticoagulants, long-term aspirin therapy, or long-term systemic steroids (greater than 3 months in the past 12 months and any within 30 days).
7. Have known hypersensitivity or allergy to eggs, egg or chicken protein or other components of the study vaccine;
8. Have a known latex allergy;

9. Have a history of severe reactions following previous immunization with licensed influenza virus vaccines
10. Have a history of Guillain-Barre syndrome
11. Subjects who had or are suspected to have had an influenza infection in the current influenza season
12. Subjects who, at screening, have abnormal vital signs and/or physical exam, including a temperature  $\geq 38.0$  C, Systolic blood pressure  $\leq 90$  or  $\geq 160$  mmHg, pulse  $\leq 60$  or  $> 110$  beats per minute, new rash, signs of infection.
13. Subjects who have already received the seasonal influenza vaccine in the current influenza vaccination season.

### **5.3 Handling of Withdrawals**

Subjects are free to withdraw from the study at any time. Subjects are provided a revocation form at enrollment with withdrawal procedures clearly explained. Subjects who have developed an adverse event or serious adverse event will be followed for safety purposes. Subjects who develop any exclusion criteria will not continue to have blood drawn. Subjects may be taken off the study without their consent if the study doctor determines that it is in his or her best interest not to continue to participate in the study, if the subject is unable to complete the required study procedures, or if the study is stopped by the Institution, the sponsor, or the Food and Drug Administration (FDA) or other health authorities. If the subject is removed from the study, the Principal Investigator or designee will contact the participant to discuss the study stopping procedures.

Participants who withdraw, or are withdrawn or terminated from the study, or are lost to follow-up after study enrollment visit will not be replaced.

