##### 3.2.2 Secondary Outcome Measures

Investigation of the longevity of humoral immunity to influenza virus in humans will be performed by:

- Measuring influenza hemagglutinin stem-specific and head-specific memory B-cells and serum antibody levels at days 0, 28, and 180.
- For serum antibody responses directed against the HA head or stem regions, we will determine the endpoint IgG titers at days 0, 28 and 180 after vaccination.  
For memory B cells, we will determine the frequency of HA head- or stem-specific IgG-secreting memory B cells per total IgG-secreting cells at days 0, 28 and 180 after vaccination.
- Plasmablast responses against either the HA head or stem antigens will be determined by direct ex vivo ELISPOT at day 7 after vaccination.
- Expression of human influenza-specific monoclonal antibodies from Day 7 plasmablasts and assessing their functional by ELISA, HAI, and virus neutralization assays.

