#### 4 STUDY DESIGN

Longitudinal assessment of the study participants will be made at every study visit. Assessments will be performed at day 0, 7, 14, 28, 90 and 180 days after immunization as outlined in the Schedule of Events (appendix A). Participants will be monitored by the study nurse for the presence of both expected reactions to vaccination and for unexpected adverse reactions for 15 minutes following vaccination. Subject enrollment will be contingent upon the availability of the seasonal flu vaccine and will end upon expiration of the product.

Due to the COVID-19 pandemic, all non-essential research was halted in mid-March 2020. New enrollments were placed on hold for this study. Follow-up visits were also halted, which impacted the timing of participants' subsequent follow-up visits. For this study, there are participants whose Day 180 visits were impacted. We will request an expansion of the study window for the participants whose Day 180 visits were impacted. Additional details regarding this are detailed further in the protocol. None of the other visits were impacted.

The clinical study is designed to characterize the specific immunologic response to influenza vaccination of humans using commercially available influenza vaccine. This study will compare and contrast the response of individual components of the immune system using licensed seasonal inactivated influenza vaccine. This vaccine is FDA approved for protection against influenza infection but may have different effects on different components of the immune system. The enrollment goal is up to a total of 70 subjects. The subjects will have blood drawn at designated time points to have ex-vivo analysis of specific immunologic responses measured. Blood will be drawn at screening, day 0, 7, 14, 28, 90 and 180 study visits.

Due to the COVID-19 pandemic, there are participants whose Day 180 visits were impacted. We are requesting that the window for the day Day 180 visit be expanded by 90 days. Day 180 is the final visit/study endpoint for this study.

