### 7.2 Enrollment/Baseline

#### Day 0 – Baseline and vaccination

- Reconfirm participant's willingness to take part in the study prior to performing any study procedures.
- Eligibility criteria, including results of all clinical screening laboratory evaluations, will be reviewed to assure continued eligibility prior to vaccination.
- All concomitant medications taken since the screening visit will be recorded on the appropriate data collection form.
- Vital signs, including oral or axillary temperature, pulse, and blood pressure, will be obtained to assure eligibility.
- In the event that the enrollment visit exceeds 14 days from screening visit, a urine pregnancy test will be performed for all females of childbearing potential, to confirm non-pregnant status.

- Approximately 48 ml of blood (3 tbsp) will be drawn from the subject prior to vaccination
- A seasonal inactivated influenza vaccine will be administered by an intramuscular injection into the deltoid muscle of the subject's preferred arm.
- The subject will be monitored for 15 minutes after vaccination to ensure that no acute reactions occur.
- Due to the COVID-19 pandemic, all non-essential research was halted in mid-March 2020. New enrollments were placed on hold for this study.

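### Section 5.3 ends blood draws for anyone who develops any exclusion criterion; this conflicts with the visit schedule and would lose late longevity samples on suspected influenza alone

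*Combined protocol and SAP*

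**What the plan says.** Section 5.3 (Handling of Withdrawals) gives the rule without exception: "Subjects who develop any exclusion criteria will not continue to have blood drawn". It adds that participants who withdraw, are withdrawn or are lost after the enrolment visit are not replaced.

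Two of the criteria in Section 5.2 matter here:
- No. 11: "Subjects who had or are suspected to have had an influenza infection in the current influenza season"
- No. 13: "Subjects who have already received the seasonal influenza vaccine in the current influenza vaccination season"

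Other criteria are tied to a time point. No. 12 begins "Subjects who, at screening, have abnormal vital signs and/or physical exam", and no. 5 covers acute illness in the 72 hours before vaccination.

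Section 7.2 gives the study vaccine to everyone at Day 0: "A seasonal inactivated influenza vaccine will be administered by an intramuscular injection into the deltoid muscle of the subject's preferred arm". Section 4 then schedules sampling for all: "Blood will be drawn at screening, day 0, 7, 14, 28, 90 and 180 study visits".

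The secondary objective is the longevity of humoral immunity. Section 3.2.2 addresses it by "Measuring influenza hemagglutinin stem-specific and head-specific memory B-cells and serum antibody levels at days 0, 28, and 180".

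The opening of Section 11 names longitudinal methods and general linear mixed models. Section 11.4 specifies a paired t-test from baseline to 4 weeks. Neither says how influenza during follow-up, or a missing late sample, is to be handled.

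**The concern.** The rule turns a list of entry conditions into a list of reasons to stop research sampling, and some entry conditions do not suit that use. Staff have to decide for themselves which criteria the rule covers, and different decisions give different late data.

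The criterion that matters in practice is no. 11. Participants with weak or quickly waning responses are plausibly more likely to catch influenza. If their draws stop, the people sampled at Day 180 lean towards those with higher titres. The loss is also irreversible: a sample taken after an infection can be left out of an analysis, but a sample never drawn cannot be recovered.

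The protocol itself values these late samples. Section 7.3 asks for a 90-day extension of the Day 180 window because even late samples would help to evaluate longevity.

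**Working it through.** The plan states no figure on this point, so there is none to reproduce. Steps 1 and 2 compare the text. Steps 3 to 6 are arithmetic on assumed inputs.

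**1. Criterion 13 against the schedule.** After Day 0 every participant has received this season's vaccine. Criterion 13 has no limit to the time before enrolment, and Section 5.3 exempts no criterion. Sections 4 and 7.3 and Appendix A nevertheless schedule draws on Days 7, 14, 28, 90 and 180 for everyone. The passages cannot all be applied as written.

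**2. Criterion 11 in follow-up.** Suspicion is enough to meet it. Section 8.1 finds illness by asking at follow-up visits, and Section 8.2 lists no influenza test. A participant who meets the criterion loses every later draw, including Day 180.

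**3. Number affected.** Attack rate *a* is assumed at 2-15%, because the documents give none. *N* is 50 (Section 11.2) or 70 (the ceiling in Section 4). Expected losses are *N* × *a*; the chance of at least one is 1 − (1 − *a*)^*N*.

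| *a* | Losses of 50 | Losses of 70 | P(at least one), *N* = 50 |
|---|---|---|---|
| 2% | 1.0 | 1.4 | 64% |
| 5% | 2.5 | 3.5 | 92% |
| 10% | 5.0 | 7.0 | 99.5% |
| 15% | 7.5 | 10.5 | >99.9% |

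**4. Bias in a simple Day 180 mean.** This is a simulation of 2,000,000 participants with every input assumed. The log2 Day 28 titre is N(6.3, SD 1.5) and the decline to Day 180 is N(1, SD 0.7). Infection risk is logistic in the mid-follow-up titre, with odds multiplied by 0.7 or 0.5 per two-fold higher titre. Bias is the mean log2 Day 180 titre of the uninfected minus the infection-free mean of everyone. The GMT ratio is 2^bias.

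| Odds ratio | Incidence | Bias (log2) | GMT too high by |
|---|---|---|---|
| 0.7 | 5 / 10 / 15% | 0.044 / 0.087 / 0.128 | 3 / 6 / 9% |
| 0.5 | 5 / 10 / 15% | 0.081 / 0.154 / 0.225 | 6 / 11 / 17% |

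**5. How much of this concerns longevity.** In the worst case (odds ratio 0.5, 15%), the uninfected are already 0.203 log2 above everyone at Day 28. Their decline is therefore understated by 0.225 − 0.203 = 0.022 log2, or 2.2% of the assumed mean decline of 1. Across all six cases the understatement is 0.4-2.2%. Regressing Day 180 on Day 28 among the uninfected and predicting at everyone's Day 28 mean leaves a GMT bias of 0.3-1.7%. This approximates what a mixed model fitted by likelihood would do.

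A harsher variant sets the Day 28 mean at 6.5 and makes infection depend on the Day 180 titre itself. The simple bias is then 3-18%, decline is understated by about 1-4%, and conditioning on Day 28 leaves 0.6-3.4%.

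**6. Scale.** The Day 180 SD is √(1.5² + 0.7²) = 1.655. With 45 of 50 sampled, the 95% half-width is 1.96 × 1.655/√45 = 0.484 log2, so the upper limit lies 2^0.484 − 1 = 40% above the GMT.

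**The case against.** A reader might infer from criterion 13 that the protocol forbids every sample after Day 0. The documents do not support that as the intended meaning. *Develop* is an odd word for receiving the study vaccine, inclusion criterion 4 states the same condition for entry, and the whole schedule assumes later draws. The conflict is real but confined to the wording.

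A reader might also infer that durability would be overstated by up to 17%. That is a shift in titre level in a simple Day 180 summary, and most of it is already present at Day 28. For persistence, or under the mixed model that Section 11 names if it is fitted by likelihood, little remains. This objection stands and limits the claim. The plan does not, however, say how the model is fitted or how missing samples are treated.

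It can fairly be said that stopping after a natural infection is a defensible design choice, because infection may boost titres and obscure the vaccine response. That is a reason to flag or exclude a sample in the analysis. It does not require that the sample never be taken, and Section 3.2.3 itself lists infected subjects among its exploratory targets. Safety does not depend on the sentence either: the rest of Section 5.3 lets the study doctor remove a participant in their best interest, and Section 9.3.1 deals with pregnancy separately.

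The number affected may be small. There is no active surveillance for influenza, and criterion 11 applies only to the current season. The primary outcome (seroconversion, Days 0 and 28) and the Day 7 plasmablast measures are less exposed.

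**Conclusion.** The point holds in a limited form. Section 5.3, read with criteria 11 and 13 of Section 5.2, conflicts with the visit schedule. For criterion 13 this is a drafting conflict to which no size should be attached. For criterion 11 the rule can realistically operate, and it then discards late longevity samples for good, on unconfirmed suspicion and without replacement.

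The number lost is unknown. On assumed inputs, a simple Day 180 GMT would be about 3-17% too high. Within-person decline, or an estimate that conditions on Day 28, would be off by about 2% or less, rising to about 4% if infection depends on the Day 180 titre itself. Direction and size both rest on the assumption that low titres raise the risk of infection. This is worth correcting because it is cheap and the lost samples cannot be recovered. It does not threaten the study.

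**What to change.** 1. **Section 5.3.** Reconcile it with Section 5.2 and the visit schedule. Replace the general reference to exclusion criteria with a named list of those that end research sampling, chosen by the investigator on safety grounds. State that receipt of the study vaccine is not one of them.
2. **Suspected influenza in follow-up.** Unless the investigator sees a safety reason to stop, keep collecting the scheduled research samples. Record the date and whether the infection was confirmed.
3. **Section 11.** Analyse longevity with the mixed model already named there, fitted by likelihood and keeping all pre-infection data from every participant. Report results with post-infection samples excluded and, as a sensitivity analysis, included.
4. **Limits to state with the results.** Excluding post-infection samples leaves the same uninfected people at Day 180, so a simple mean would keep its bias; the protection comes from the model's use of earlier data. Including them may add infection-boosted titres. An assumed four-fold boost (2 log2) at 5-15% incidence raises the GMT by 2^(2 × 0.05) − 1 = 7% to 2^(2 × 0.15) − 1 = 23%. Neither version fully recovers the infection-free titre.

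The cost is an amended sentence, two data items (date and confirmation), one extra analysis, and a few assayed samples that may be left out of the main estimate.

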### **5.4 Termination of Study**

The sponsor reserves the right to terminate the study at any time for clinical or administrative reasons.

## 6 STUDY INTERVENTION PRODUCT

### 6.1 Study Product Description

Each flu season, the vaccine used in this study will be a licensed seasonal inactivated influenza vaccine that is approved by the FDA for the current flu season. The vaccine product used will depend upon supply stocked by the Emory University Hospital Investigational Drug Services (IDS). These vaccines are typically provided in pre-filled syringes (clear syringe plunger rod), 0.5 ml. If pre-filled syringes are not available from the manufacturer, the study product will be provided in a latex free vial, 5 ml, one vial per carton.

#### 6.1.1 Acquisition

The licensed vaccine will be provided by the Emory University Hospital Investigational Drug Pharmacy and will be stored in a secure temperature-monitored refrigerator in a secure, limited access storage area.

#### 6.1.2 Formulation, Packaging, and Labeling

The vaccine used in this study is the licensed seasonal inactivated influenza vaccine and will be supplied by Emory University Hospital Investigational Drug Services (IDS) in a pre-filled syringe placed in a clear plastic bag labeled with the DMID protocol number, study ID, and dosing instructions per the prescription signed by [name] or a designee.

#### 6.1.3 Product Storage and Stability

Per the package insert from the manufacturer, the seasonal inactivated influenza vaccine will be stored at 2-8 degrees C (35-45 degrees F) in a study specific designated location in a refrigerator at the Emory University Hospital Investigational Drug Services. The refrigerator temperature is monitored via the Temp Trak system, an electronic temperature monitoring system that records temperatures every five minutes 24 hours a day. The refrigerator is set to alarm at 2.5 degrees C or 7.5 degrees C. If there is a deviation in temperature, the Temp Trak system will notify the Emory IDS pharmacist via an alarm system.

## **6.2 Dosage, Preparation and Administration of Study Intervention Product**

Upon receipt of the signed prescription, an Emory IDS pharmacist will prepare the study drug and, per standard operating procedure, will have a 2nd pharmacist double check the study prescription with the study product and label before dispensing the drug to the clinical research nurse for administration. An Emory IDS pharmacist or pharmacy technician will walk over the study product to the clinic procedure area and then deliver it to the research coordinator. The pharmacist or pharmacy technician will hand the subject's medication to the clinical research nurse who will then verify the correct protocol, subject name and study ID, study product, dosing instructions per signed prescription, and study product expiration date using a checklist.

A vaccine dose of 0.5 mL will be administered by qualified personnel at the GCRC intramuscularly (IM) in the subject's preferred arm per the manufacturer's instructions.

## **6.3 Accountability Procedures for the Study Intervention Product(s)**

The Emory Investigational Drug Service will maintain and monitor the inventory of the influenza vaccine per their standard operating procedures (SOPs).

## **6.4 Assessment of Participant Compliance with Study Intervention Product**

Each participant will be assessed for compliance with the influenza vaccination via his or her receipt of 0.5ml of vaccine without immediate reaction.

## **6.5 Concomitant Medications/Treatments**

Subjects with chronic medical conditions or taking medications that are prohibited according to Section 5.2 Exclusion Criteria will be excluded from study participation. The medication history will be reviewed and updated at every study visit to ensure that subjects are not taking the medications prohibited for study participation. Subjects will be allowed to take anti-pyretics (e.g. acetaminophen) and/or non-steroidal anti-inflammatories (NSAIDs; e.g. ibuprofen) after vaccination if desired by subject.

## 7 STUDY SCHEDULE

### 7.1 Screening (Day -1 to day -30)

Potential participants will be screened for eligibility within 30 days prior to the administration of the study product. Screening period begins at screening visit and continues through enrollment visit. Qualified subjects will be scheduled for enrollment visit 1-day post screening visit through 30 days post screening visit. At screening, the following activities will be performed:

- Participants will be provided with a description of the study (purpose and study procedures) and asked to read and sign the informed consent form. The informed consent form will be signed prior to performing any study procedures, including any screening procedures.
- Complete medical history will be obtained by interview of participants to assure eligibility, including history of prior influenza vaccinations.
- All concomitant medications will be recorded on the appropriate data collection form.
- Demographic information will be collected from the participant.
- Eligibility criteria will be reviewed.
- A urine pregnancy test will be performed on all female participants of childbearing potential and must be negative.
- Approximately 16 ml (about 1 tablespoon) of venous blood will be collected for chemistry and hematology performed by the site laboratory. The results will be provided by the site laboratory and be reviewed by the principal investigator.
- Targeted physical exam, including height, weight and vital signs (oral or axillary temperature, pulse, blood pressure.).

### 7.2 Enrollment/Baseline

#### Day 0 – Baseline and vaccination

- Reconfirm participant's willingness to take part in the study prior to performing any study procedures.
- Eligibility criteria, including results of all clinical screening laboratory evaluations, will be reviewed to assure continued eligibility prior to vaccination.
- All concomitant medications taken since the screening visit will be recorded on the appropriate data collection form.
- Vital signs, including oral or axillary temperature, pulse, and blood pressure, will be obtained to assure eligibility.
- In the event that the enrollment visit exceeds 14 days from screening visit, a urine pregnancy test will be performed for all females of childbearing potential, to confirm non-pregnant status.

- Approximately 48 ml of blood (3 tbsp) will be drawn from the subject prior to vaccination
- A seasonal inactivated influenza vaccine will be administered by an intramuscular injection into the deltoid muscle of the subject's preferred arm.
- The subject will be monitored for 15 minutes after vaccination to ensure that no acute reactions occur.
- Due to the COVID-19 pandemic, all non-essential research was halted in mid-March 2020. New enrollments were placed on hold for this study.

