## 5 STUDY POPULATION

The study will enroll 10 healthy volunteers per vaccination season in years 1, 2, and 4, to analyze the immune response to influenza vaccination in healthy individuals. For years 5 and 6, we anticipate enrolling a maximum of 20 participants, to analyze the immune response to influenza vaccination in healthy individuals.

Total enrollment goal is up to a total of 70 subjects. Individuals who complete the study will be given the option to re-enroll in subsequent years as long as they continue to meet all inclusion/exclusion criteria. Re-enrolling subjects will be re-consented, given new subject identifiers, and counted towards the enrollment number goal for each year of participation.

- Males and non-pregnant females confirmed to be non-pregnant immediately prior to vaccination, aged 18 - 49, inclusive.
- Study subjects will be drawn from existing populations of students, staff, faculty, or volunteers at Emory University or other eligible healthy adults who may hear of the study by word of mouth.
- Study subjects will be recruited via word of mouth and placement of recruitment flyers in key locations on campus. Social media messaging via Facebook and Twitter will also be used in an effort to increase the number of enrollees into this study.

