### 5.1 Inclusion Criteria

For inclusion into the study, a subject must satisfy all of the following criteria:

1. Male or female subjects between 18 and 49 years of age, inclusive
2. Subjects capable of providing written informed consent prior to initiation of any study procedures. Subjects able to understand and comply with planned study procedures and be available for all study visits
3. Screening labs within normal limits per the local laboratory normal ranges or considered to be not clinically significant by the investigator. Normal laboratory ranges are as listed below:
  - A. Hematology:
    - Hemoglobin: Male- 12.9-16.1 gm/dL, Female- 11.4-14.4 gm/dL
    - White blood cells (WBC): Male- 4.2-9.2/uL, Female- 4-10/uL
    - Platelet count: 150-400/uL
  - B. Chemistries:
    - Kidney function:Glomerular filtration rate (GFR) >/= 60 mL/min/1.73 m^2;

- Liver enzymes: Albumin  $\geq 3.5$  g/dL; ALT  $<66$  U/L; AST  $<62$  U/L
- 4. Subjects who have not received the seasonal influenza vaccine in the current flu season and are not suspected to have had an influenza infection in the current flu season.
- 5. Female subjects of child bearing potential must have a negative urine pregnancy test at the screening visit, enrollment visit and all subsequent study visits longer than 14 days since the last pregnancy test.

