### 7.3 Follow-up and Final Visits

#### Follow-up visits: Days 7, 14, 28, 90, 180.

- Study participants will be asked to return for five follow up visits, with the respective window periods, per the table below:

Day	7	14	28	90	180
Time point					
Window	+/- 1	+/- 2	+/- 3	+/- 10	+/- 14 (a 90 day window expansion is being requested)
Blood Volume	96mL	96mL	64mL	64mL	64mL

- Medical history will be reviewed and updated as appropriate.
- All concomitant medications taken since the previous study visit will be recorded on the appropriate data collection form. Previously recorded medications will be updated as appropriate.
- Study personnel will discuss with participants and assess and record all AE/SAEs. Previously recorded AE/SAEs will be updated as appropriate.
- Approximately the amount of venous blood, as indicated by the table above, will be collected for research assays.
- Targeted physical exam will be done only as dictated by a change in medical history.
- A urine pregnancy test will be performed on all female participants of childbearing potential

for any visit longer than 14 days from the last pregnancy test..

- Follow-up visits were also halted, which impacted several participants' Day 180 follow-up visit.
- We are requesting that the windows for the Day 180 visit be extended by 90 days.
- Extending the window for the Day 180 follow-up visits would allow samples from participants whose visits were halted at this time point to be collected once the Emory restrictions regarding COVID-19 are lifted and staff can reasonably collect samples, dependent upon when the University and applicable Unit and School allow. The scientists feel that the samples, even if a few months late, will greatly help evaluate the longevity of the responses to flu vaccines.
- Study activities will not be changed, just the timing of the Day 180 visit.

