## 8 STUDY PROCEDURES AND EVALUATIONS

### 8.1 Clinical Evaluations

- Clinical interview of subject at screening to include:
  - Demographics: age, date of birth, gender, ethnicity, race
  - History of allergies: food, drug, environmental, specifically solicit if any allergy to vaccines or eggs
  - History of influenza vaccination, and previous reactions, if any
  - History of Guillain-Barre syndrome
  - History of medications taken within the past 90 days to include prescription and over the counter medications, specifically solicit if any blood thinners or immunosuppressive agents have been used
  - History of any vaccinations within the past year
  - Acute or chronic medical conditions as reported by subject
- Vital signs (blood pressure, pulse, temperature, height, weight)
- Targeted physical exam
- Collection of blood for clinical laboratory tests at screening visit (16 ml)
- Collection of research blood samples at study visits: day 0 (48 ml), 7, 14 (96 ml), 28, 90 and 180 (64 ml).
- Administration of licensed seasonal inactivated influenza vaccine by the clinical research nurse at Day 0
- Clinical health assessment at follow up study visit to include inquiry regarding any illness, any change in medication, and any overall health changes since last study visit.
- A urine pregnancy test will be performed on all female participants of childbearing potential and must be negative.

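### Section 5 and inclusion criterion 5 look for confirmation of non-pregnancy at enrollment, but Section 7.2 requires no Day 0 test when screening was 14 days earlier or less

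*Combined protocol and SAP*

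**What the plan says.** Two parts of the protocol set who may be vaccinated. Section 5 describes the females in the population as "confirmed to be non-pregnant immediately prior to vaccination". Inclusion criterion 5 in Section 5.1 says that women of childbearing potential "must have a negative urine pregnancy test at the screening visit, enrollment visit and all subsequent study visits longer than 14 days", counted from the last pregnancy test.

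Three places set what the site does. Section 7.2, which lists the Day 0 procedures, says: "In the event that the enrollment visit exceeds 14 days from screening visit, a urine pregnancy test will be performed". Section 9.3.1 requires a test at screening and then only at visits falling more than 14 days after the previous test, with no separate rule for Day 0. A footnote to Appendix A refers to women whose enrollment visit comes more than 14 days after screening.

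The interval between the two visits is fixed by Section 7.1: "Qualified subjects will be scheduled for enrollment visit 1-day post screening visit through 30 days post screening visit".

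Three other statements bear on the point. Section 7.2 also says: "Eligibility criteria, including results of all clinical screening laboratory evaluations, will be reviewed to assure continued eligibility prior to vaccination". Exclusion criterion 2 bars a woman in these terms: "If female, active pregnancy or breast-feeding or plans to become pregnant during study participation". Section 8.1 says: "A urine pregnancy test will be performed on all female participants of childbearing potential and must be negative", without naming a visit.

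**The concern.** A site that follows Section 7.2 to the letter can vaccinate a woman with no test on the day, while Section 5 and, as naturally read, criterion 5 call for her status to be established at that visit. Whether she is tested depends on which section the coordinator opens.

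What is at stake is the last eligibility and safety check before dosing. There is also a compliance question. Section 14.6 sends deviations related to subject safety or eligibility to the IRB under its guidelines, and lists the reported ones for DMID. The same conduct could count as an eligibility deviation under criterion 5 and as correct practice under Section 7.2.

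**Working it through.** The protocol gives no figure of its own to reproduce here. The check is a comparison of texts and one count.

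**Which rule applies to Day 0**

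| Place | What it requires at Day 0 | 14-day condition? |
|---|---|---|
| Section 5 | Non-pregnancy confirmed just before vaccination; no method named | No |
| Criterion 5 | Negative urine test at enrollment, on the natural reading | Only on the alternative reading |
| Section 7.2 | Urine test | Yes |
| Section 9.3.1 | Urine test | Yes |
| Appendix A footnote | Urine test, by its wording | Yes |
| Section 8.1 | Urine test, no visit named | Silent |

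**Two readings of criterion 5.** The sentence lists screening, enrollment and all later visits, and then adds the 14-day qualifier.

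- If the qualifier belongs to the last item only, the enrollment test is unconditional and conflicts with Sections 7.2 and 9.3.1.
- If it reaches back to the enrollment visit, criterion 5 agrees with Section 7.2. The conflict with Section 5 remains. Section 7.2 gives confirming non-pregnant status as the purpose of its urine test, and no other method of confirmation appears. A result up to 14 days old does not confirm status just before vaccination.

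**Whether other text closes the gap.** The pre-vaccination eligibility review in Section 7.2 catches an untested woman only if criterion 5 is taken on its first reading, which is the question at issue. Exclusion criterion 2 names no test. Section 8.1 names no visit.

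**Size of the gap**

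- Permitted screening-to-enrollment intervals (Section 7.1): 1 to 30 days, so 30 intervals.
- Intervals that do not exceed 14 days (threshold in Section 7.2): 1 to 14 days, so 14 intervals.
- Share with no Day 0 test under Section 7.2: 14/30 = 46.7%.
- Oldest result on which a woman can be vaccinated: 14 days.
- With an unconditional Day 0 test: 0 of 30.

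**A knock-on effect at Day 7.** Section 7.3 requires a test "for any visit longer than 14 days from the last pregnancy test". If Day 0 is skipped, a woman screened 8 to 14 days before Day 0 reaches a nominal Day 7 visit with a result 8 + 7 = 15 to 14 + 7 = 21 days old. Section 7.3 then calls for a Day 7 test, but the Appendix A cell is blank. If Day 0 is always tested, the latest Day 7 visit (window of 1 day) falls 7 + 1 = 8 days after a test, and the blank cell is right.

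**The case against.** The best reply is that the procedural text is consistent. Sections 7.2 and 9.3.1 and the Appendix A footnote all make the enrollment test conditional, and Section 7.3 carries the same 14-day logic forward. The conditional rule is probably what was intended. Criterion 5 can be read to agree with it, which leaves one descriptive bullet in Section 5 that names no test. On this view it is enough to reword Section 5 and criterion 5, and a Day 0 test for everyone is a preference.

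Much of that is fair. The likely intent and the second reading of criterion 5 both stand, and so does the point that rewording would restore consistency. Nothing in the documents shows that a result up to 14 days old is inadequate. But the Section 5 clash survives that reading, and the text as it stands gives sites two rules.

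The stake is also small. The vaccine is licensed and given as standard of care, a negative screening test is mandatory, exclusion criterion 2 applies, and Section 9.3.1 follows any pregnancy to its outcome.

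Four stronger readings are tempting, and the documents do not support them:

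- A reader might infer that nearly half of the women would be vaccinated without a Day 0 test. The 47% counts calendar intervals. The protocol gives neither the number of women of childbearing potential nor the actual intervals.
- A reader might infer that Section 5 itself demands a urine test on the day. It demands confirmation and names no test.
- A reader might take the Appendix A mark at Day 0 as an unconditional test that contradicts the footnote. The footnote marker is not visible in the extracted table, so neither its link to the Day 0 cell nor an unconditional mark can be established.
- A reader might conclude that the Day 14 and Day 28 entries in the grid must be changed too. They do not bear on the enrollment conflict.

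**Conclusion.** The inconsistency is real and minor. Under Sections 7.2 and 9.3.1, a woman enrolled 1 to 14 days after screening can be vaccinated with no Day 0 test. She then does not meet Section 5 or, on its natural reading, criterion 5. This covers 14 of the 30 permitted intervals, with a result at most 14 days old at vaccination.

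The conclusion about criterion 5 rests on reading its qualifier as attached to the later visits only. The conclusion about Section 5 rests on the urine test being the only means of confirmation the protocol offers. How many participants are affected cannot be stated.

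The sample size reasoning and the analyses in Section 11 do not depend on the point. It merits correction because an eligibility check before dosing should follow one rule and the correction is cheap.

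**What to change.** - **Section 7.2:** require a negative urine pregnancy test on Day 0, before vaccination, for all women of childbearing potential, and delete the condition that enrollment be more than 14 days after screening.
- **Appendix A footnote:** delete the same condition.
- **Criterion 5 and Section 9.3.1:** state that screening and Day 0 are always tested and that the 14-day rule applies only to visits after Day 0.

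Section 5 then needs no change, and no edit to the Day 14 or Day 28 entries is needed to resolve the conflict.

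The cost is the protocol wording and one extra urine test, of a kind already in the study, for women screened 1 to 14 days before enrollment.

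The alternative is to keep the conditional rule and reword Section 5 and criterion 5 to match it. That adds no Day 0 test, but it settles for the weaker check before vaccination and leaves the Day 7 mismatch for women screened 8 to 14 days earlier unless the grid is edited too.
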